10.9 Obligations of Investigators

The Principal Investigator is responsible for the conduct of the clinical trial at the site in accordance with Title 21 of the Code of Federal Regulations and/or the Declaration of Helsinki. The Principal Investigator is responsible for personally overseeing the treatment of all study patients. The Principal Investigator must assure that all study site personnel, including sub-investigators and other study staff members, adhere to the study protocol and all FDA/GCP/NCI regulations and guidelines regarding clinical trials both during and after study completion.

The Principal Investigator at each institution or site will be responsible for assuring that all the required data will be collected and entered onto the Case Report Forms. Periodically, monitoring visits will be conducted and the Principal Investigator will provide access to his/her original records to permit verification of proper entry of data. At the completion of the study, all case report forms will be reviewed by the Principal Investigator and will require his/her final signature to verify the accuracy of the data.

10.10 Publications of Data and Protection of Trade Secrets

The Principal Investigator (Protocol Chair) holds the primary responsibility for publication of the study results; provided that the PI will provide Exelixis with a copy of any proposed publication or release: (a) for abstracts, slide presentations or posters, at least five (5) business day prior to submission (in the case of abstracts) or first public presentation (in the case of slide presentations and posters); and (b) at least thirty (30) days in advance of first submission and each subsequent submission in the case of manuscripts and also comply with any provisions regarding publication that are agreed to between the PI's institution (eg, institution name.) and Exelixis, Inc. in the Clinical Trial Agreement related to this study.

10.11 Conditions for Terminating the Study

At any time, the study may be terminated by the study sponsor, the sponsoring institution, or by Exelixis. Should this be necessary, Exelixis and the investigator will arrange the procedures on an individual study basis after review and consultation. In terminating the study, Exelixis and the investigator will ensure that adequate consideration is given to the protection of the subjects' interests. Upon study termination, the investigator(s) shall cease enrolling subjects into the study, and shall discontinue conduct of the study as soon as is medically practicable.

12.0 APPENDICES

APPENDIX A

Performance Status Criteria

E	ECOG Performance Status Scale		Karnofsky Performance Scale
Grade	Descriptions	Percent	Description
	Normal activity. Fully active, able	100	Normal, no complaints, no evidence of disease.
0	to carry on all pre-disease performance without restriction.	90	Able to carry on normal activity; minor signs or symptoms of disease.
1	Symptoms, but ambulatory. Restricted in physically strenuous activity, but ambulatory and able	80	Normal activity with effort; some signs or symptoms of disease.
l	to carry out work of a light or sedentary nature (e.g., light housework, office work).	70	Cares for self, unable to carry on normal activity or to do active work.
2	In bed <50% of the time. Ambulatory and capable of all self-care, but unable to carry out	60	Requires occasional assistance, but is able to care for most of his/her needs.
any work activities. Up and about more than 50% of waking hours.	50	Requires considerable assistance and frequent medical care.	
3	In bed >50% of the time. Capable of only limited self-care,	40	Disabled, requires special care and assistance.
confined to bed or chair more than 50% of waking hours.	30	Severely disabled, hospitalization indicated. Death not imminent.	
4	100% bedridden. Completely disabled. Cannot carry on any	20	Very sick, hospitalization indicated. Death not imminent.
4	self-care. Totally confined to bed or chair.	10	Moribund, fatal processes progressing rapidly.

CONFIDENTIAL

Protocol #: UCI 18-124 MP 10/11//2022

	5	Dead.	0	Dead.	1
Ш	0	Dodd.	0	Dodd.	

APPENDIX B

Pill Diary

Cabozantinib Patient Pill Diary			
Patient Name: MRN: Cycle:			
Cabozantinib will be taken daily at home, except for clinic days when it will be taken at the clinic.			
Taketablet(s) of 20mg Cabozantinib tablets once daily every 21 days.			
Cabozantinib will be taken at least one hour before or at least two hours after eating.			
If doses of cabozantinib are missed or held, do not make up for missed doses.			
Take each dose as close to the same time every day as possible.			
Please record the date and time you take Cabozantinib.			
Please remember to bring your bottles and Patient Pill Diary at each clinic visit.			
Date Time Number of Pills Taken/ Comments			
· · · · · · · · · · · · · · · · · · ·			
Day 1 tablet(s) taken Day 2 tablet(s) taken			
Day 3tablet(s) taken			
Day 4tablet(s) taken			
Day 5tablet(s) taken			
Day 6tablet(s) taken			
Day 7tablet(s) taken			
Day 8 tablet(s) taken			
Day 9 tablet(s) taken			
Day 10 tablet(s) taken			
Day 11 tablet(s) taken			
Day 12 tablet(s) taken			
Day 13 tablet(s) taken			
Day 14 tablet(s) taken			
Day 15 tablet(s) taken			
Day 16 tablet(s) taken			
Day 17 tablet(s) taken			
Day 18tablet(s) taken			
Day 19tablet(s) taken			
Day 20 tablet(s) taken Day 21 tablet(s) taken			

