² estimated from stratified Cox proportional hazards model with stratification factors IMDC risk group and presence of bone metastases and treatment as covariate

³ two-sided stratified log-rank test with stratification factors IMDC risk group and presence of bone metastases

⁴ no multiplicity adjustments were made for overall survival or ORR

[figure not shown]

Figure 5: Overall Survival in CABOSUN (ITT)

How Supplied / Storage Handling

Cabozantinib tablets are supplied as film coated tablets containing cabozantinib malate equivalent to 20 mg of cabozantinib and contain microcrystalline cellulose, lactose anhydrous, hydoxypropyl cellulose, croscarmellose sodium, colloidal silicon dioxide, magnesium stearate and Opadry® yellow. The 60-mg tablets are oval and the 20-mg tablets are round. Doses of 40 mg will comprise two 20-mg tablets. The components of the tablets are listed in Table 4.

Table 4: Cabozantinib Tablet Components and Composition

Ingredient	Function	% w/w ^a
Cabozantinib Drug Substance (25% drug load as free base)	Active Ingredient	31.68
Microcrystalline Cellulose (Avicel® PH-102)	Filler	38.85
Lactose Anhydrous (60M)	Filler	19.42
Hydroxypropyl Cellulose (EXF)	Binder	3.00
Croscarmellose Sodium (Ac-Di-Sol®)	Disintegrant	6.00
Colloidal Silicon Dioxide	Glidant	0.30
Magnesium Stearate	Lubricant	0.75
Opadry® yellow film coating which includes HPMC 2910/hypromellose 6 cp, titanium dioxide, triacetin, and iron oxide yellow	Film Coating	4.00

^aweight fraction, expressed in percentage; HPMC, hydroxypropyl methylcellulose

Cabozantinib Administration

Subjects will receive cabozantinib orally at a (starting) dose of 40 mg once daily. Cabozantinib must be taken on an empty stomach. Subjects must be instructed not to eat for at least 2 hours before and at least 1 hour after taking cabozantinib. Subjects should be instructed to take their cabozantinib dose at approximately the same time every day. If a subject misses a dose, the dose may be taken later only if it is within 12 hours of when the missed dose should have been taken. The missed dose should not be made up if it is within 12 hours of the next scheduled dose.

Cabozantinib tablets should be swallowed whole with at least 8 ounces of water. The tablets should not be crushed. Grapefruit, grapefruit juice, Seville oranges and their products should be avoided by subjects taking cabozantinib.

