4.2 Toxicities and Dosing Delays/Dose Modifications

Any patient who receives treatment on this protocol will be evaluable for toxicity. Each patient will be assessed for the development of toxicity according to the Time and Events table (Section 5.5). Toxicity will be assessed according to the NCI Common Toxicity Criteria for Adverse Events (CTCAE), version 5.0. Dose adjustments should be made according to the system showing the greatest degree of toxicity.

Cabozantinib and pembrolizumab have class specific safety profiles based on their mechanism of action but may also cause AEs that overlap. For management of AEs which can be clearly attributed to cabozantinib or pembrolizumab, independent dose modification for either agent is allowed. Examples of VEGFR TKI associated AEs caused by cabozantinib are hypertension and hand-foot syndrome. Examples of immune-related AEs caused by pembrolizumab are pneumonitis and endocrinopathies. For AEs without clear attribution to either study treatment, management of toxicity should include dose modifications of both agents per the discretion of the investigator. Examples of overlapping AEs are diarrhea and transaminase increases.

Protocol #: UCI 18-124 MP 10/11//2022

Dose Modification Table

Dose Level	Agent	Dose
1 (starting dose)	Cabozantinib	40 mg
1 (starting dose)	Pembrolizumab	200 mg
-1 (50% reduction)	Cabozantinib	20 mg
-2	Cabozantinib	20 mg every other day

Toxicities:

Toxicity Dose Reductions			
NCI CTC Grade	Cabozantinib	Pembrolizumab	
Grade 0-2	No change from original starting dose	No change from original starting dose (unless described in 4.2.1)	
Intolerable grade 2 or grade 3	Hold until resolved to < Grade 1 then resume to dose level 1 or -1, depending on physician assessment	Hold until resolved to < Grade 2, then resume at dose level 1 (unless described in 4.2.1)	
Second episode of grade 3 or intolerable grade 2 first episode of grade 4 toxicity	Hold until resolved to ≤ Grade 1 then reduce to dose level one less than previous (i.e1 or -2) Discontinue permanently (unless investigator determines patient is deriving clear clinical benefit)	Discontinue permanently (unless described in 4.2.1)	
Third episode of grade 3	Remove subject from trial	Not applicable	

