Patients will receive instructions for home administration of cabozantinib according to the regimen description above. Cabozantinib is to be taken 1 hour before or 2 hours after meals. If doses of cabozantinib are missed or held, the patient should not make up for the missed doses.

Patients will be given a study medication diary to complete at home for cabozantinib. Compliance with the dosing regimen will be assessed based on completion of the drug diary and return of unused drug (or empty bottles).

IMP Destruction

IMP will be destroyed by the sponsor according to their SOPs. Destruction logs should be made available to Exelixis at the end of the study.

IMP Returns

Exelixis will not accept returned IMP

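### The Appendix B pill diary prints a daily frequency that cannot express dose level -2 in Section 4.2, and the protocol gives two different missed-dose rules

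*Combined protocol and SAP*

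**What the plan says.** **Frequency.** The dose modification table in Section 4.2 gives cabozantinib 40 mg as the starting level, 20 mg as level -1 (labelled a 50% reduction), and "20 mg every other day" as level -2. Appendix B contains the only diary in the documents. Its dosing line has a place for the number of tablets, followed by the printed words "20mg Cabozantinib tablets once daily every 21 days". Another line repeats the frequency: "Cabozantinib will be taken daily at home, except for clinic days when it will be taken at the clinic". A third asks for each dose at about the same time every day. Below are rows for Days 1 to 21.

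**Missed doses.** Under Cabozantinib Administration in Section 1.2, when a dose is missed, "the dose may be taken later only if it is within 12 hours of when the missed dose should have been taken"; the next sentence bars making it up within 12 hours of the next scheduled dose. Section 8.1 says: "If doses of cabozantinib are missed or held, the patient should not make up for the missed doses". The diary agrees with Section 8.1: "If doses of cabozantinib are missed or held, do not make up for missed doses".

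**Use of the diary.** Section 8.1 has patients complete the diary at home and assesses compliance from the diary together with returned drug or empty bottles.

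**The concern.** Cabozantinib is taken at home, and the diary is a written dosing instruction that the patient keeps. A patient moved to level -2 has already been reduced for toxicity. For that patient the form, used exactly as printed, describes a schedule other than the one in the protocol's own table.

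Other rules depend on which dose was actually taken. Section 5.6 stops study treatment in a subject who cannot tolerate the minimum protocol-specified dose, so it matters whether that dose was ever received. Section 7.5 gives a wrong dosage as an example of a violation, reportable within 24 hours to the coordinating center and within 5 business days to the DSMB. A patient who obeyed the printed form could generate such a report.

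On missed doses, a patient or site can follow one section and breach another. A skipped or late dose in the diary then does not show whether the patient departed from instructions or followed a different section.

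**Working it through.** The documents give no figure of their own to reproduce. The check is a side-by-side reading with a tablet count.

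**1. Frequency**

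Inputs: 21-day cycle with daily dosing on days 1-21 (Section 4.1.1); 20-mg tablets, two making a 40 mg dose (Section 1.2); level -2 on alternate days (Section 4.2); printed daily frequency (Appendix B).

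- Diary with one tablet entered: 21 days × 1 tablet = 21 tablets; 21 × 20 mg = 420 mg per cycle.
- Section 4.2 level -2, starting on day 1 (days 1, 3, ..., 21): 11 tablets; 11 × 20 mg = 220 mg.
- Section 4.2 level -2, starting on day 2 (days 2, 4, ..., 20): 10 tablets; 10 × 20 mg = 200 mg.
- Ratio, diary to table: 420/220 = 1.9 up to 420/200 = 2.1. Over two consecutive cycles of strict alternation it is 42/21 = 2.0.

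One tablet under the printed line is 20 mg daily. That is the amount at level -1, if level -1 is read as daily because it is labelled half of 40 mg daily. Entering two tablets gives the starting dose. No entry in the tablet field gives an alternate-day schedule, so the diary can express the starting level and level -1 but not level -2.

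**2. Missed doses**

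Take a dose scheduled at 08:00 with the next due at 08:00 the following day.

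- Remembered at 14:00: 6 hours late and 18 hours before the next dose. Section 1.2 permits it; Section 8.1 and the diary do not.
- Remembered at 22:00: 14 hours late and 10 hours before the next dose. Section 1.2 also excludes it, so all three agree.

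The disagreement therefore covers the first 12 hours after the scheduled time. It cannot be removed by saying that a late dose is not a made-up dose, because Section 1.2 itself uses that term for the same missed dose. Section 8.1 and the diary also mention held doses; the missed-dose sentences in Section 1.2 do not, so no conflict arises there.

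The diary and Section 8.1 are on the same side. This split lies within the protocol body, and editing the diary alone would leave it in place.

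**3. Effect on the analysis**

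Section 6.1.1 counts a patient as evaluable once cycle 1, day 1 is received, and Section 9.3 plans no analysis by compliance. The two-stage design in Section 9.2 uses neither quantity. Sample size and error rates do not change.

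**The case against.** The strongest reply is that doubled intake at level -2 is a worst case. Section 8.1 also provides instructions for home administration, drug accountability is reviewed before each cycle (Section 5.3.1), and a coordinator can write on a form. This stands as a limit on the size of the problem. It does not remove it: Section 8.1 ties those instructions to the regimen description, the regimen table in Section 4.1.1 lists only the 40 mg daily dose, and no section tells staff to amend the diary after a reduction. Accountability would show 21 against 10 or 11 tablets, but only after the cycle.

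It is also fair that compliance does not rest on the diary alone, since returned drug is counted, and that few patients are likely to reach level -2.

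A reader might infer three further conflicts, which the documents do not support:

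- **Fasting.** Section 1.2 says "Subjects must be instructed not to eat for at least 2 hours before and at least 1 hour after taking cabozantinib"; the diary says "Cabozantinib will be taken at least one hour before or at least two hours after eating". Eating at 8, dosing at 9 and eating at 10 would satisfy the second only if its word for the alternative is treated as a loophole. Read naturally, Sections 4.1.1 and 8.1 and the diary describe the same window as Section 1.2, seen from the meal rather than from the dose.
- **Size of a food effect.** The increases of 41% in Cmax and 57% in AUC in Section 1.2 come from a single 140 mg dose of an investigational capsule in healthy subjects, high-fat meal against fasting. They do not measure a difference between these wordings for tablets starting at 40 mg.
- **The 21-day phrase in the dosing line.** With a cycle field and 21 daily rows on the same form, it is a clumsy cycle label, not a rival schedule.

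**Conclusion.** Two internal inconsistencies hold and should be fixed. First, the diary cannot state dose level -2. Taken literally with one tablet, it directs 1.9 to 2.1 times the tablets per cycle that the Section 4.2 table gives. Second, Section 1.2 conflicts with Section 8.1 and Appendix B on a missed dose remembered within 12 hours.

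The first conclusion assumes that the tablet number is the only dosing entry left open, as the text indicates, and that the form is issued without correction. How often level -2 is used is not stated; among at most 27 patients it is probably rare. It would go too far to infer that patients will in fact receive double the tabled dose, that the diary alone is at fault on missed doses, or that the primary result is threatened. The consequences are for patient safety at level -2 and for the interpretation of exposure and compliance data. Nothing here says which schedule or missed-dose rule is right.

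**What to change.** 1. Reconcile the Section 4.2 dose table with Appendix B so that the diary can state the frequency for every dose level the protocol permits.
2. Reconcile the missed-dose wording across Section 1.2, Section 8.1 and Appendix B, and carry the single agreed wording into the diary. The sponsor decides which rule stands.
3. In the same revision, use one fasting wording in Sections 1.2, 4.1.1 and 8.1 and Appendix B. This is a drafting clarification only.

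The cost is a revised one-page form, matching edits to the protocol text, and IRB approval of a patient-facing document. Under Section 10.7, protocol amendments also need the drug supplier's review and approval. No change to the design, sample size or analysis is needed.
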